Secondary Objectives	
To assess the effect of treatment with deferasirox combined with erythropoietin and erythropoietin alone on hematological response within 24 weeks of treatment in patients randomized to combination therapy at baseline defined by hemoglobin, platelets and neutrophil levels.
 
To assess the effect of treatment on erythropoiesis after 24 weeks in patients that were non-responder to erythropoietin alone after 12 weeks and switched to combination of deferasirox combined with erythropoietin defined by hemoglobin levels.
 
To assess the effect of treatment with erythropoietin alone on erythropoiesis after 24 weeks of treatment defined by hemoglobin levels.
 
To assess time to erythroid response in patients treated with deferasirox combined with erythropoietin and patients treated with erythropoietin alone.
 
To estimate time to erythroid response in patients who were non-responder to erythropoietin alone after 12 weeks and switched to combination of deferasirox combined with erythropoietin.
 
To estimate time to hematological response in patients treated with deferasirox combined with erythropoietin and erythropoietin alone in 24 weeks.
 
To estimate duration of erythroid response among responders treated with deferasirox combined with erythropoietin or erythropoietin alone.
 
To evaluate tolerability and safety of the combination by incidence of adverse events (AEs) overall and by severity, and serious adverse events (SAEs).

	
To assess iron parameters in patients randomized to erythropoietin alone, deferasirox combined with erythropoietin and in patients randomized to erythropoietin and switched to deferasirox combined with erythropoietin after 12 weeks by change in serum ferritin from baseline to every visit throughout the study.
 
To assess hemoglobin parameters in patients randomized to erythropoietin alone, deferasirox combined with erythropoietin and in patients randomized to erythropoietin and switched to deferasirox combined with erythropoietin after 12 weeks by change in hemoglobin from baseline to every visit throughout the study.

Study design	This is an open-label, phase II, randomized, multi-center, pilot study in patients with low- and int-1-risk myelodysplastic syndrome. 60 Patients will be randomly assigned to deferasirox plus erythropoietin or to erythropoietin alone in a 1:1 ratio. The study treatment duration is 24 weeks.

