4.1 Description of study design

This is an open-label, phase II, randomized, multi-center, pilot study to assess the efficacy in terms of erythroid improvement of DFX combined with EPO compared to EPO alone in patients with low- and int-1-risk MDS.

Patients will be randomly assigned to DFX plus EPO 40,000 units/week or to EPO 40,000 units/week alone in a 1:1 ratio. The dose of DFX DT will be 10 mg/kg/day and the dose of DFX FCT will be 7 mg/kg/day. At the time when DFX FCT study drug becomes available at a study site, all new patients who are randomized to combination therapy will receive the DFX FCT. Patients who are ongoing and receive DFX DT will continue with the DT. It is not permitted to change formulation during treatment. EPO dose changes after 4 and 12 weeks of study treatment will also be performed in both arms according to the EPO guidelines.

If after 4 weeks, increase in Hb is < 1 g/dL and total Hb is < 12 g/dL, the EPO dose will be increased to 60,000 units/week. If increase in Hb is ≥ 1 g/dL and total Hb is < 12 g/dL, patients will continue the current EPO dose. If Hb increase is ≥ 1 g/dL and total Hb is ≥ 12 g/dL, the patients will hold EPO treatment until end of study (Table 4-1).

If after 12 weeks of treatment with EPO alone, Hb increase is < 1 g/dL and total Hb is < 12 g/dL, the patient will switch to the combination therapy with EPO and DFX. If increase in Hb is ≥ 1 g/dL and total Hb is < 12 g/dL, patients will continue the current EPO dose. If Hb increase is ≥ 1 g/dL and total Hb is ≥ 12 g/dL, the patients will hold EPO treatment until end of study (Table 4-1).

[figure not shown]
If after 12 weeks of treatment with EPO in combination with DFX, Hb increase is < 1 g/dL and total Hb is < 12 g/dL, the patient will be discontinued from the study. If increase in Hb is ≥ 1 g/dL and total Hb is < 12 g/dL, patients will continue the current EPO dose plus DFX. If Hb increase is ≥ 1 g/dL and total Hb is ≥ 12 g/dL, the patients will hold EPO dose and receive treatment with DFX alone.

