As the EPO guidelines only provide guidance for EPO use (EPO dosing, dose adjustments and dose discontinuation) and do not specify any criteria for the evaluation of erythroid response in MDS patients, in this study, the primary objective erythroid response will be assessed according to IWG criteria (Hb increase ≥ 1.5 g/dL) at 12 weeks of treatment. At any time, if Hb ≥ 12 g/dL, EPO will be stopped until the end of study. Patients treated with the combination therapy will stop EPO if Hb ≥ 12 g/dL and continue on DFX.

At 24 weeks, patients initially assigned to the combination therapy who showed Hb increase ≥ 1 g/dL at week 12 will be assessed for full hematological response according to IWG criteria (Erythroid response: Hb increase from baseline ≥ 1.5 g/dL; Neutrophil response: increase from baseline of $\geq 100\%$ and $> 0.5 \times 10^9/L$; Platelet response: increase from baseline of $\geq 30 \times 10^9/L$).

Patients initially treated with EPO alone and switched to the combination therapy with EPO and DFX after 12 weeks will be assessed for erythroid response at study end after 24 weeks of study treatment.

Figure 4-1 Study Design

Pre-treatment phase (Screening)

At Screening Visit (Visit 1) the investigator or his/her designee will assign a unique number to patients being considered for the study.

Prior to performing any study-related procedures or assessments, the patient must provide written consent to participation in this study. A screening period (up to 28 days) will be used to assess patient eligibility. Two Screening Visits will be required because key safety parameters need to be performed twice before the first dose administration ([Table 7-1](#)).

This study will use an Interactive Web Response (IWR) technology for randomization. Once the patient provides a signed informed consent form and eligibility is confirmed (all inclusion/exclusion criteria have been verified) the investigator and/or his designee can register the patient using the IWR.

Treatment phase

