2.9.2 Secondary objectives

The following secondary endpoints will be analyzed by treatment arms.

2.9.2.1 To assess the effect of treatment with DFX+EPO and EPO alone on hematologic response within 24 weeks of treatment

This analysis includes patients who were randomized to EPO and EPO+DFX and remained in their respective treatment arms.

Hematological response will be assessed on this subset of patients and hematological responder is defined as patient meeting at least one of the following modified IWG 2006 criteria:

Hematological response:

- Hb increase from baseline ≥ 1.5 g/dL and Hb < 11 g/dL at baseline (All patients on study per inclusion criterion 5, cf. study protocol section 5.2).
- Neutrophil response: increase from baseline of $\geq 100\%$ and increase $> 0.5 \times 10^9$ /L and neutrophils $< 1.0 \times 10^9$ /L at baseline.
- Platelet response: increase from baseline of $\geq 30 \times 10^9$ /L and platelets $< 100 \times 10^9$ /L at baseline.

Patients who met at least one of the 3 conditions of hematological response at any time between first day of treatment and week 12 or 24 will be considered as responders.

Supportive analyses (proportion of patients, descriptive statistics on the related parameters, change from baseline) will also be provided for patients who do not satisfy the IWG 2006 pre-treatment conditions for neutrophil and/or platelet response (i.e., these patients have baseline neutrophils $\geq 1.0 \times 10^9$ /L and baseline platelets $\geq 100 \times 10^9$ /L) but show hematologic improvement with respect to neutrophils (increase from baseline $> 0.5 \times 10^9$ /L) and/or platelets (increase from baseline $\geq 30 \times 10^9$ /L).

Proportion of patients achieving a hematological response within 12 weeks and within 24 weeks of treatment with DFX combined with EPO and EPO alone will be calculated along with 95% Clopper-Pearson confidence interval. Descriptive statistics will be provided for

hematological improvement response, as well as for all hematological improvement of myeloid cell lineages subcomponents (hemoglobin, erythrocytes, neutrophils and platelets). Analysis will be performed on FAS.

Hematologic response and improvement within 12 weeks and 24 weeks will be analyzed separately.

Table 2-2 summarizes the distinction between response and improvement as being used for supportive analyses:

Table 2-2 Criteria for hematological response and hematologic improvement

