2.11 CSR Section 9.7.2: Sample size and power considerations

This is a pilot study that was planned to enroll approximately 60 patients considering site capabilities. No formal sample size calculation based on primary endpoint assumptions is performed.

However to give an idea regarding primary endpoint analysis, for a given number of 60 patients, under scenarios, where considering a minimal detectable differences of 20%, 30% and 40% assuming a reference response rate of 40% at 5% level of significance gives a 95% Agresti-Caffo confidence interval of (-0.04, 0.44), (0.068, 0.53) and (0.18, 0.62).

Clinical Development

ICL670

CICL670A2421

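### The 24-week hematological response has no settled denominator: DFX+EPO patients who must leave at week 12 are in or out depending on the sentence followed, and under assumed models the rate moves by about 6 to 31 points

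*SAP*

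**What the plan says.** Four statements bear on who is counted.

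- **Week-12 exit.** For the combination arm, Protocol 4.1 and Table 4-1 state: "Hb increase is < 1 g/dL and total Hb is < 12 g/dL, the patient will be discontinued from the study". In the EPO arm the same Hb finding leads to a switch to DFX+EPO.
- **Design text.** On the 24-week assessment, Protocol 4.1 has this: "patients initially assigned to the combination therapy who showed Hb increase ≥ 1 g/dL at week 12 will be assessed for full hematological response". Protocol 6.1.4 carries the same sentence with *by* week 12 in place of *at*.
- **Analysis text.** SAP 2.9.2.1, like Protocol 10.5.1, says: "This analysis includes patients who were randomized to EPO and EPO+DFX and remained in their respective treatment arms". Response is then assessed on that subset.
- **Analysis set.** The same two sections place the analysis on the FAS, which Protocol 10.1.1 and SAP 2.3 define as everyone randomised.

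Scoring within the set is written. Under SAP 2.9.2.1, patients who meet a criterion "at any time between first day of treatment and week 12 or 24 will be considered as responders". SAP 2.5 takes percentages over all patients in the relevant population or subgroup, and SAP 4.6 allows no imputation unless stated. A patient who is in the set and met no criterion is therefore a non-responder.

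**The concern.** The planned exit removes combination patients because their Hb rise was small, and an Hb rise of at least 1.5 g/dL is one of the three response criteria. Dropping these patients removes mostly non-responders from the denominator and almost nothing from the numerator. The result would still be reported as the response within 24 weeks of DFX+EPO on the FAS, although the denominator could consist largely of patients already known to have improved. Two programmers could follow the text faithfully and report different rates from the same data.

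SAP 2.9.2.1 also reports a 12-week hematological rate on the same subset. If the leavers are out, that rate has a different denominator from the primary 12-week erythroid rate (SAP 2.9.1.2, FAS), although erythroid response is a component of both.

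**Working it through.** **Inputs from the documents.** There are 60 patients at 1:1, so 30 per arm. SAP 2.11 illustrates the primary endpoint "assuming a reference response rate of 40% at 5% level of significance", with differences of 20, 30 and 40 points, so the DFX+EPO week-12 rates are 60%, 70% and 80%. The plan states no rate, interval or share of leavers for the 24-week endpoint, so there is no figure of its own to reproduce. The intervals in SAP 2.11 concern the 12-week endpoint and do not bear on this point.

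**The exit rule.** Baseline Hb is capped at about 10.5 g/dL (10 plus the 5% tolerance in inclusion criterion 5). Reaching 12 then needs a rise of at least 12 − 10.5 = 1.5, so in practice the rule is a week-12 rise below 1 g/dL.

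**Who is in, by wording**

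| Wording | Combination leavers | EPO switchers |
|---|---|---|
| Protocol 4.1 (*at* week 12) | out | not addressed |
| Protocol 6.1.4 (*by* week 12) | in only if +1 g/dL was reached earlier | not addressed |
| *Remained* = stayed 24 weeks | out | out |
| *Remained* = did not switch | in | out |
| FAS | in | in |

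**Calculation 1: normal model (assumed).** Let the week-12 rise be normal with SD 0.75 to 2.0 g/dL, let r be the share with a rise of at least 1.5, and let f be the share of the 1–1.5 g/dL band that responds after week 12. Leavers are taken as non-responders.

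- Mean rise: μ = 1.5 − SD × Φ⁻¹(1 − r)
- Share staying: s = 1 − Φ((1 − μ)/SD)
- Rate with leavers kept: r + f(s − r)
- Rate with leavers dropped: [r + f(s − r)]/s

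Example with r = 0.60, SD = 1.5, f = 0.5: μ = 1.5 + 1.5 × 0.253 = 1.88; s = 1 − Φ(−0.587) = 0.721; kept = 0.60 + 0.5 × 0.121 = 66.1%; dropped = 0.661/0.721 = 91.6%.

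| Week-12 rate | f = 0: kept vs dropped | f = 0.5 | f = 1 |
|---|---|---|---|
| 60% | 60 vs 73–87 | 65–71 vs 87–93 | 69–82 vs 100 |
| 70% | 70 vs 79–90 | 74–79 vs 90–95 | 78–88 vs 100 |
| 80% | 80 vs 86–93 | 83–87 vs 93–96 | 86–93 vs 100 |

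The smallest gap is 85.6 − 80.0 = 5.6 points (80%, SD 0.75, f = 0). The largest is 100 − 69.3 = 30.7 points (60%, SD 2.0, f = 1).

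**Calculation 2: visit-level simulation (assumed).** 200,000 patients; baseline Hb 8–10; within-patient SD 0.4; between-patient SD of the plateau rise 0.8, 1.2 or 1.6; linear rise to day 70; Hb at days 14, 28, 56, 84, 112, 140 and 168. It is calibrated to the week-12 rate and counts Hb responses only. Leavers are scored on their values up to day 84.

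| Week-12 rate | Leave at week 12 | All randomised | Stayers only | Gap |
|---|---|---|---|---|
| 60% | 26–32% | 65–68% | 91–94% | 23–29 points |
| 80% | 11–14% | 84–86% | 96–97% | 10–14 points |

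At the 60% scenario, 13–22% of leavers had reached +1 g/dL earlier, so 6.1.4 would keep them and 4.1 would not.

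**At the trial's arm size.** Take 20 responders among 30 with 8 leavers, none of whom responded. Leavers kept: 20/30 = 66.7% (Clopper-Pearson 47.2–82.7%). Leavers dropped: 20/22 = 90.9% (70.8–98.9%).

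**EPO arm.** With EPO at the plan's 40%, EPO non-switchers show about 85–90% at 24 weeks in the simulation. Putting only DFX+EPO on all randomised would set 65–68% beside 85–90%. With both arms on all randomised, the normal model at SD 1.5 and f = 0.5 gives 66.1% against 46.6%, a difference of 19.5 points, close to the assumed 20.

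**The case against.** The best case for the plan is that *remained* most naturally means *did not switch*. The parallel EPO analysis in SAP 2.9.2.3 is framed that way, and combination patients have nothing to switch to. On that reading the week-12 leavers are already in, and the scoring rule makes them non-responders unless they met a criterion. Support for the completer reading is indirect: the SAP 2.7.2 note concerns EPO exposure, and the Table 3-1 entries that speak of patients throughout in an arm belong to the ferritin and Hb-change endpoints. Protocol 4.1 and 6.1.4 are design and treatment text, not the analysis section. The endpoint is descriptive, with one-arm intervals in a pilot study, and the primary FAS analysis already gives an unselected erythroid rate at 12 weeks.

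Much of this stands, and it rules out several stronger readings that a reader might infer:

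- *Leavers have no scoring rule.* They have one once they are in the set; only membership is open.
- *Both 4.1 and 6.1.4 drop every leaver.* Only 4.1 does; *by* week 12 keeps some.
- *The rate is about 66% or 93%.* The documents contain neither figure. That pair needs about 29% leaving (1 − 0.66/0.93) and no response among leavers. An earlier Hb rise, or a platelet or neutrophil response, can make a leaver a responder.
- *Only the combination arm is affected.* The EPO subset is selected by the same cut-off.

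The objection does not remove the conflict. Protocol 4.1 states who is assessed at 24 weeks, that set is selected on Hb rise, and it cannot be squared with the FAS.

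**Conclusion.** The point holds as a contradiction about set membership. Followed as written, Protocol 4.1 conditions the DFX+EPO denominator on a component of the outcome. The *remained* condition does the same if it means 24-week completers, and it does not if it means non-switchers. The FAS label contradicts 4.1 and the completer reading for the combination arm, and contradicts either reading of *remained* for EPO switchers.

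The inflation of the DFX+EPO rate is about 6 to 31 points over week-12 rates of 60–80%. It is largest when week-12 response is low and shrinks as response rises. The range rests on assumed Hb variability and late-response shares and leaves out platelet and neutrophil responses, so it shows scale and is not a forecast. The EPO rate is selected in the same way, so the subset rates should not be compared between arms. The primary 12-week analysis is not touched.

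**What to change.** In SAP 2.9.2.1 and Protocol 10.5.1, state one rule for **both** arms:

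- The denominator is all randomised patients (FAS).
- Combination patients discontinued at or before week 12 are scored on all values up to their end-of-treatment visit.
- EPO patients who switch are scored on all values up to the switch.
- In either case a patient who met no criterion is a non-responder.

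Reconcile the *at* and *by* week-12 wording in Protocol 4.1 and 6.1.4 with this rule as far as it describes who is analysed. The treatment, switch and discontinuation rules stay as they are. If the *remained* rate is kept, define the word, show that rate second for both arms, and label it as selected on week-12 Hb and not comparable between arms.

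Changing the combination arm alone should be avoided: as shown above, it could make the better arm look about 20 points worse.

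The cost is wording in two documents. No new data are needed, since hematology is already scheduled at the week-12 and end-of-treatment visits (Protocol Table 7-1, SAP Table 4-1). The headline rates in both arms become less favourable. Responses that EPO switchers achieve after the switch are not lost, because SAP 2.9.2.2 reports their erythroid response separately.

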To estimate duration of erythroid response among responders treated with EPO alone	Duration of erythroid response is defined as the time from onset of the first response to progression/relapse (decrease in Hb \geq 1.5 g/dL from Hb value at response) among responders treated with EPO alone within the whole 24 weeks period	Refer to Section 10.5.7

Objective	Endpoint	Analysis
To estimate duration of erythroid response among responders treated with DFX+EPO	Duration of erythroid response is defined as the time from onset of the first response to progression/relapse (decrease in Hb \geq 1.5 g/dL from Hb value at response) among patients randomized to EPO+DFX up to week 24 and for patients switched from EPO to DFX+EPO from week 13 to week 24	Refer to Section 10.5.8
To evaluate tolerability and safety of the combination	Incidence of adverse events (AEs) overall and by severity, and serious adverse events (SAEs).	Refer to Section 10.5.11
To assess iron parameters in patients randomized to EPO alone, DFX+EPO and in patients randomized to EPO alone and switched to DFX+EPO after 12 weeks	Change in SF from baseline to every visit in patients throughout in the combination arm, throughout in the EPO arm and switched from EPO arm to EPO+DFX after 12 weeks	Refer to Section 10.5.9
To assess Hb parameters in patients randomized to EPO alone, DFX+EPO and in patients randomized to EPO alone and switched to DFX+EPO after 12 weeks	Change in Hb from baseline to every visit in patients throughout in the combination arm, throughout in the EPO arm and switched from EPO arm to DFX+EPO after 12 weeks	Refer to Section 10.5.10
Supportive		
To assess the effect of treatment with DFX+EPO and EPO alone on hematologic improvement within 24 weeks of treatment	Proportion of patients achieving a hematologic improvement (improvement of neutropenia and thrombocytopenia) within 24 weeks of treatment with DFX+EPO and EPO alone	Refer to Section 10.5.1
To assess the effect of treatment with DFX+EPO and EPO alone on total hematological response within 24 weeks of treatment	Proportion of patients achieving a hematological response (increase in Hb, improvement of neutropenia and thrombocytopenia) according to modified IWG 2006 criteria and patients achieving a hematologic improvement (improvement of neutropenia and thrombocytopenia) within 24 weeks of treatment with DFX+EPO and EPO alone	Refer to Section 10.5.1

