To estimate time to hematologic improvement in patients treated with DFX+EPO and EPO alone within 24 weeks	Time to hematologic improvement is defined as the time from date of start of treatment to the date of event defined as the first documented hematologic improvement (improvement of neutropenia and thrombocytopenia)	Refer to Section 10.5.6
To estimate time to total hematological response in patients treated with DFX+EPO and EPO alone within 24 weeks	Time to total hematological response is defined as the time from date of start of treatment to the date of event defined as the first documented hematologic improvement (improvement of neutropenia and thrombocytopenia) or hematological response (increase in Hb, improvement of neutropenia and thrombocytopenia) according to modified IWG 2006 criteria	Refer to Section 10.5.6

4 Study design

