Hematological response: If a patient fulfills at least erythroid or platelet or neutrophil response as well as it's corresponding pre-treatment condition	Hb < 11 g/dL at baseline Platelet $< 100 \times 10^9/L$ at baseline Neutrophil $< 1.0 \times 10^9/L$ at baseline	Hb increase from baseline by ≥ 1.5 g/dL Increase from baseline $\geq 30 \times 10^9/L$ Increase from baseline $> 100\%$ and increase from baseline $> 0.5 \times 10^9/L$	Erythroid response Platelet response Neutrophil response
Hematologic improvement: If a patient fulfills at least platelet or neutrophil improvement response without it's corresponding pre-treatment condition	Platelet $\geq 100 \times 10^9/L$ at baseline Neutrophil $\geq 1.0 \times 10^9/L$ at baseline	Increase from baseline $\geq 30 \times 10^9/L$ Increase from baseline $> 0.5 \times 10^9/L$	Platelet improvement Neutrophil improvement

10.5.2 To assess the effect of treatment on erythropoiesis within 24 weeks in patients who were non-responder to EPO alone after 12 weeks and switched to DFX+EPO

Patients who are non-responders to erythroid at week 12 in the EPO group will have to switch to combination therapy, if they continue to participate in the study.

Patients meeting the criterion (Hb increase from baseline ≥ 1.5 g/dL) at any time between week 12 and week 24 will be considered as erythroid responders.

Proportion of erythroid responders between week 13 and 24 will be reported along with its 95% Clopper-Pearson confidence interval. Descriptive statistics will be provided for erythroid response. Analysis will be performed on FAS and PP set.

10.5.3 To assess time to erythroid response in patients treated with DFX+EPO and patients treated with EPO alone

This analysis will include patients who were randomized to EPO and EPO+DFX and remained in their respective treatment arms. Descriptive statistics will be provided for erythroid responder patients (achieved Hb increase ≥ 1.5 g/dL from baseline) for time to response (days), defined as the time from date of start of treatment to the date of event defined as the first documented erythroid response between week 1 to week 24. Analysis will be performed on FAS and PP set for both treatment groups.

10.5.4 To assess the effect of treatment with EPO alone on erythropoiesis after 24 weeks of treatment

[figure not shown]
This analysis includes patients who started with the EPO alone and are not switched to combination therapy.

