Further descriptive statistics on time to neutrophil and platelet improvement for patients who did not satisfied pre-treatment IWG criteria but show hematologic improvement according to modified IWG response criteria:

- Neutrophil improvement: increase from baseline $> 0.5 \times 10^9/L$
- Platelet improvement: increase from baseline of $\geq 30 \times 10^9/L$

will be provided along with summary on total time to hematological response ([Section 10.5.1](#)). Such analysis will be done for patients remaining in the EPO+DFX arm and EPO alone arm.

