	Pre-treatment conditions	Post-baseline	Response
Hematological response: If a patient fulfills at least erythroid or platelet or neutrophil response as well as it's corresponding pre-treatment condition	Hb < 11 g/dL at baseline	Hb increase from baseline by ≥ 1.5 g/dL	Erythroid response
	Platelet < 100×10^9 /L at baseline	Increase from baseline $\geq 30 \times 10^9$ /L	Platelet response
	Neutrophil < 1.0×10^9 /L at baseline	Increase from baseline > 100% and increase from baseline > 0.5×10^9 /L	Neutrophil response
Hematologic improvement: If a patient fulfills at least hemoglobin or platelet or neutrophil improvement response without it's corresponding pre-treatment condition	Hemoglobin < 11 g/dL at baseline	Increase from baseline by ≥ 1 g/dL	Hemoglobin improvement
	Platelet $\geq 100 \times 10^9$ /L at baseline	Increase from baseline $\geq 30 \times 10^9$ /L	Platelet improvement
	Neutrophil $\geq 1.0 \times 10^9$ /L at baseline	Increase from baseline > 0.5×10^9 /L	Neutrophil improvement

2.9.2.2 To assess the effect of treatment on erythropoiesis within 24 weeks in patients who were non-responder to EPO alone after 12 weeks and switched to DFX+EPO

Patients who are non-responders to erythroid at week 12 in the EPO group will have to switch to combination therapy, if they continue to participate in the study.

Patients meeting the criterion (Hb increase from baseline ≥ 1.5 g/dL) at any time between week 12 and week 24 will be considered as erythroid responders.

Proportion of erythroid responders between week 13 and 24 will be reported along with its 95% Clopper-Pearson confidence interval. Descriptive statistics will be provided for erythroid response. Analysis will be performed on FAS.

2.9.2.3 To assess the effect of treatment with EPO alone on erythropoiesis within 24 weeks of treatment

This analysis includes patients who started with the EPO alone and are not switched to combination therapy.

Patients meeting the criterion (Hb increase from baseline ≥ 1.5 g/dL) at any time between week 1 and week 24 will be considered as erythroid responders. Proportion of erythroid responders who starts with EPO alone and are not switched to combination therapy will be reported along with its 95% Clopper-Pearson confidence interval.

Descriptive statistics will be provided for erythroid response. Analysis will be performed on FAS.

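### The SAP's added Hb row makes hematologic improvement automatic for EPO patients who stay in arm past week 12, and the neutrophil and platelet rows count unconfirmed rises in patients without the cytopenia

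*SAP*

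**What the plan says.** Protocol Table 3-1 lists as a supportive endpoint the "Proportion of patients achieving a hematologic improvement (improvement of neutropenia and thrombocytopenia) within 24 weeks". It then pools this with IWG hematological response as a total hematological response, both as a proportion and as a time to event ("Time to total hematological response is defined as the time from date of start of treatment" to the first of either event).

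Protocol Table 10-1 sets the criterion: "If a patient fulfills at least platelet or neutrophil improvement response without it's corresponding pre-treatment condition". There are two rows:
- platelets at least 100 x 10^9/L at baseline, with a rise of at least 30;
- neutrophils at least 1.0 x 10^9/L at baseline, with a rise above 0.5.

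Protocol 10.5.6 repeats the thresholds ("Neutrophil improvement: increase from baseline" by more than 0.5).

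SAP Table 2-2 changes the definition to "If a patient fulfills at least hemoglobin or platelet or neutrophil improvement response without it's corresponding pre-treatment condition" and adds a third row: Hb below 11 g/dL at baseline, "Increase from baseline by ≥ 1 g/dL". The sentence in SAP 2.9.2.1 that says who enters this supportive analysis does not mention Hb. It covers patients who "show hematologic improvement with respect to neutrophils (increase from baseline" above 0.5) and/or platelets. A later sentence names hemoglobin among the lineages to be described, without a threshold.

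The analysis is restricted to patients who stayed in their randomised arm (protocol 10.5.1, SAP 2.9.2.1). At week 12, an Hb rise below 1 g/dL with Hb below 12 g/dL means a switch in the EPO arm and discontinuation in the combination arm. Otherwise treatment goes on; for the combination arm, protocol 4.1 says "If increase in Hb is ≥ 1 g/dL and total Hb is < 12 g/dL, patients will continue the current EPO dose plus DFX".

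**The concern.** There are two separate problems.

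First, the SAP's Hb row is filed under a heading for patients who do not meet the pre-treatment condition, yet its entry condition is that same condition. It overlaps with erythroid response, so the table no longer separates response from improvement. It also uses the threshold that selects the analysed subset, so among EPO patients past week 12 it carries no information.

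Second, the endpoint is named as improvement of neutropenia and thrombocytopenia, but the rows admit only patients above the IWG cut-offs for those cytopenias. A platelet change from 220 to 251, or neutrophils from 3.0 to 3.6, would qualify on one reading.

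In an open-label pilot of about 60 patients, such proportions could be read as multilineage benefit. Depending on who counts as having stayed in arm, they could also show a difference between arms that the drug did not cause.

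**Working it through.** The documents give no expected rate for improvement, so there is no planning figure to reproduce.

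**1. Hb row in the EPO arm (document figures only).** A patient is switched if the rise is below 1 and Hb is below 12. A patient correctly not switched therefore has one of the following:
- a rise of at least 1 g/dL, which meets the row directly; or
- Hb of at least 12. Inclusion criterion 5 allows Hb below 10 with a 5% tolerance, so baseline is at most 10 x 1.05 = 10.5, and the rise is at least 12 - 10.5 = 1.5 g/dL. This also meets the row.

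The rate is 100%, whatever the effect of deferasirox. This assumes that baseline Hb lies within the entry limits, that the same baseline is used for the rule and the analysis, and that the switch rule was followed. Patients who leave before week 12 are not covered.

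**2. Hb row in the combination arm.** If patients discontinued at week 12 are dropped, the same argument gives 100%. If they stay in the denominator, the rate is at least the probability of passing the rule. Assume a mean EPO-driven rise m with between-patient SD s, visit-to-visit Hb SD e, and no deferasirox effect:

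P(pass) is about 1 - Φ((1 - m) / √(s² + 2e²))

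- m = 0.7, s = 1.0, e = 0.3: 1 - Φ(0.3/1.086) = 39%.
- m = 1.0: 50%.

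Counting a rise at any visit, simulation gave 42 to 58% for the Hb row (m 0.7 or 1.0, s 1.0 or 1.2, e 0.3 or 0.5). The full SAP composite was 49 to 87%, against 100% in EPO stayers. The documents do not say which denominator applies.

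**3. Neutrophil and platelet rows with no true change.** The hematology schedule gives seven post-baseline counts by week 24 (weeks 2, 4, 8, 12, 16, 20, 24), plus one if Visit 8 takes place. With independent normal errors, SD = CV x mean and threshold t:

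P(at least one rise above t in k counts) = 1 - ∫ φ(x) Φ(x + t/SD)^k dx

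Example, k = 7:
- neutrophils 2.5, CV 15%: SD 0.375, t/SD = 1.33, P = 50%;
- platelets 200, CV 10%: SD 20, t/SD = 1.5, P = 45%;
- either: 1 - 0.50 x 0.55 = 72%.

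Baselines and CVs below are assumptions. The table shows the share with either rise, k = 7:

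| Baseline neutrophils / platelets | CV 5/5% | 10/8% | 15/10% | 20/10% | 25/12% |
|---|---|---|---|---|---|
| 1.5 / 120 | 0% | 11% | 36% | 49% | 63% |
| 2.0 / 150 | 1% | 30% | 57% | 67% | 77% |
| 2.5 / 200 | 9% | 52% | 72% | 79% | 85% |
| 3.0 / 220 | 16% | 62% | 79% | 83% | 88% |

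Positive correlation between visits would lower these figures. If both lineages must rise, the example falls to 0.50 x 0.45 = about 22%.

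**4. Effect of a duration rule.** Appendix 2 heads its criteria with a duration of at least 8 weeks. Requiring the rise at every scheduled count over such a span changes the no-change rate as follows:
- 2.0/150, CV 10/8%: 30% to 2%
- 2.0/150, CV 15/10%: 57% to 7%
- 2.5/200, CV 15/10%: 73% to 14% (simulated; 72% by the formula)
- 2.5/200, CV 25/12%: 85% to 25%

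No duration rule rescues the Hb row while its threshold equals the stay-in-arm threshold.

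**The case against.** A reader might infer that most patients will improve with no treatment effect. The documents do not support that. They give neither within-patient variability nor a distribution of baseline counts. The table runs from 0% to 88%, and several plausible cells lie well below half. The Hb row is not pure fluctuation either: both arms receive EPO, so a rise of 1 g/dL reflects EPO and selection. Noise alone over seven counts gives only 5, 16 and 29% at an Hb SD of 0.3, 0.4 and 0.5 g/dL.

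A reader might also say that the neutrophil row drops a doubling that Appendix 2 requires. Appendix 2 sets that doubling only for baseline neutrophils below 1.0, so nothing it requires was removed for these patients. Nor are all the counts normal: SAP Table 2-4 flags neutrophils below 1.5 as notable, while the improvement floor is 1.0.

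The Hb row is not shown to enter total hematological response. That endpoint is defined in the protocol, whose improvement criterion has no Hb row, and the SAP efficacy text does not specify it.

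Finally, the analysis is labelled supportive, IWG response is defined separately with its pre-treatment conditions, and change from baseline is already planned. All of this stands and limits the weight of the point. It does not remove the contradiction in Table 2-2, the overlap with the stay-in-arm rule, or the mismatch between label and criterion.

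**Conclusion.** The SAP's Hb row is wrong as written. It departs from protocol Table 10-1, contradicts its own heading, double-counts erythroid responders, and is met by 100% of EPO patients correctly kept in arm past week 12. That result needs only the documents' figures and the assumptions in step 1. Whether it yields two uninformative rates or an artificial gap against the combination arm depends on a denominator that the SAP leaves open.

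The neutrophil and platelet rows are mislabelled and unconfirmed. The share they would count with no true change is unknown: from about 10% or less to about 90% under the assumptions shown. The documents do not settle where in that range the trial would fall.

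Only supportive outputs are affected. The primary endpoint and the IWG hematological response definition are not.

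**What to change.** - Delete the Hb row from SAP Table 2-2. Alternatively, report Hb rises of 1.0 to below 1.5 g/dL separately in all FAS patients by randomised arm, bearing in mind that after week 12 the EPO arm includes patients who switched.
- Do not pool improvement with IWG response as total hematological response (protocol Table 3-1, including the time-to-event version).
- Relabel the neutrophil and platelet rows as a count rise in patients without the IWG cytopenia.
- Reconcile the wording on whether one or both lineages must rise: protocol 10.5.1 text says and, protocol Table 10-1 says or, SAP 2.9.2.1 text says and/or.
- Describe these patients mainly by change from baseline, or count a rise only if it is sustained over the 8 weeks that head Appendix 2.

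The cost is one revised table, some wording in both documents, and lower supportive rates. With the sustained rule, a rise first seen after week 16 (24 - 8) could not be confirmed within the study. The neutrophil and platelet changes are more open to debate than the removal of the Hb row.
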